3.2 Number of Subjects

Up to 85 evaluable subjects may be enrolled across the study.

Phase 2a (PLX2853 monotherapy):

There will be up to 2 Simon's 2-stage design cohorts of up to 38 evaluable subjects with ARID1A mutation-positive (with and without PIK3CA, PIKR1, and/or PTEN mutations) advanced gynecological malignancies. The safety lead-in of 6 subjects dosed at the level selected for Phase 2a will be included in the group of 12 evaluable subjects for Stage 1.

Phase 1b (PLX2853 + carboplatin combination):

Approximately 9 to 15 evaluable subjects with platinum-resistant EOC will be enrolled, depending on the number of escalation cohorts investigated. Up to 6 additional subjects with a known ARID1A mutation (unless otherwise approved by the Medical Monitor) may be treated at the RP2D at the discretion of the Sponsor for dose confirmation purposes.

Phase 2a (PLX2853 + carboplatin combination):

There will be 1 Simon's 2-stage design cohort of between 12 to 26 evaluable subjects with platinum-resistant EOC.

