After dosing has been completed in each cohort, safety, PK, and PDx data (if available) will be reviewed, and dose escalation decisions will be made by the Study Committee. Dose escalation decisions will also take into consideration safety information beyond the DLT period from earlier cohorts. If no DLT is observed, the recommended dose for further evaluation may be established based on toxicity, PK, convenience of dosing, and PDx (if available) in subjects treated at that dose. Dose escalation will only be permitted if adequate safety and tolerability have been demonstrated at the previous lower dose for 28 days. PLX2853 and carboplatin may not be dose escalated in the same cycle.

PLX2853 PK data will be analyzed in each dosing cohort for C_{max}, AUC, and accumulation ratio at steady state and compared with prior dose levels. The number of subjects at a given dose level may be increased as a result of the review of safety, observed or anticipated disease activity, and PK data. Additional dosing schedules may be studied, such as alternate day dosing (e.g., every other day) depending on emerging safety and PK data. In Phase 2a (dose expansion), efficacy as well as additional safety, PK, and PDx data of PLX2853 in combination with carboplatin at the RP2D dose established in Phase 1b by the

Number of Subjects:

Total number of subjects: up to 85 evaluable subjects

Phase 2a (PLX2853 monotherapy): Up to 38 evaluable subjects

Study Committee will be obtained using a Simon's 2-stage design.

There will be up to 2 Simon's 2-stage design cohort of up to 38 evaluable subjects with ARID1A mutation-positive (with and without PIK3CA, PIK3R1, and/or PTEN mutations) advanced gynecological malignancies. The safety lead-in of 6 subjects dosed at the level selected for Phase 2a will be included in the group of 12 evaluable subjects for Stage 1.

Phase 1b (PLX2853 + carboplatin combination): Up to 21 evaluable subjects

Approximately 9 to 15 evaluable subjects with platinum-resistant EOC will be enrolled, depending on the number of escalation cohorts investigated. Up to 6 additional subjects with a known ARID1A mutation (unless otherwise approved by the Medical Monitor) may be treated at the RP2D at the discretion of the Sponsor for dose confirmation purposes.

Phase 2a (PLX2853 + carboplatin combination): Up to 26 evaluable subjects

There will be 1 Simon's 2-stage design cohort of between 12 to 26 evaluable subjects with platinum-resistant EOC.

Inclusion Criteria:

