The study will employ a standard 3 + 3 design in order to determine the MTD/RP2D taking into consideration safety, PK, and PDx data (if applicable).

Data will be tabulated and evaluated by descriptive statistics. Statistical analyses for the primary objectives will be descriptive only, with no hypothesis testing. Summary tables will present results for each dose cohort. Descriptive statistics will be presented for continuous variables, and frequencies and percentages will be presented for categorical and ordinal variables.

Response to treatment will be evaluated by investigator-determined response using RECIST v1.1 criteria.

Phase 2a (PLX2853 Monotherapy) and Phase 2a (PLX2853 + carboplatin combination):

The primary objectives of the Phase 2a cohorts of the study are to determine the antitumor activity (ORR) of PLX2853 monotherapy or PLX2853 + carboplatin combination. Response to treatment will be evaluated using investigator-determined RECIST v1.1 criteria, with a minimum interval for confirmation of CR and PR of 4 weeks. Each Phase 2a cohort will enroll up to 26 evaluable subjects using a Simon's 2-stage design in which initially 12 evaluable subjects are enrolled. In the monotherapy cohort, the safety lead in of 6 subjects dosed at the level selected for Phase 2a will be included in the group of 12 evaluable subjects for stage 1. If \geq 33% DLTs are seen during the initial safety lead in, the Safety Committee will convene to consider a dose reduction. If a dose reduction is deemed appropriate, the subjects in the initial safety lead in will need to be replaced and a repeat 6 subject safety lead in will need to be conducted at this lower dose. If 2 or more responses are observed in 12 evaluable subjects, another 14 evaluable subjects will be enrolled for a total of 26 subjects to that cohort. If 6 or more responses are observed, the study has 80% power with alpha of 0.05 to reject the ORR of 10% in favor of the ORR of 30%. Recruitment will stop within a cohort if no more than 1 response is observed after the initial 12 evaluable subjects have been accrued. ORR will be summarized per cohort along with their 95% confidence intervals (CIs). A 2-sided 95% CI will be calculated for the true response rate based on the Clopper Pearson method.

PLX2853 Protocol PLX124-03/Amendment 2

SYNOPSIS TABLE 1: PHASE 2A PLX2853 MONOTHERAPY SCHEDULE OF EVENTS

ASSESSMENTS ▼	PROCEDURE ▼	SCR1	C1		C2	C3+ ²					

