8.6.2 Phase 2a (PLX2853 Monotherapy) and Phase 2a (PLX2853 + Carboplatin Combination)

8.6.2.1 Primary Efficacy Analysis

The primary objectives of the Phase 2a cohorts of the study are to determine the antitumor activity (ORR) of PLX2853 monotherapy or PLX2853 + carboplatin combination. Response to treatment will be evaluated using investigator-determined RECIST v1.1 criteria (Appendix 3), with a minimum interval for confirmation of CR and PR of 4 weeks. Each Phase 2a cohort will enroll up to 26 evaluable subjects using a Simon's 2-stage design in which initially 12 evaluable subjects are enrolled. In the monotherapy cohort, the safety lead in of 6 subjects dosed at the level selected for Phase 2a will be included in the group of 12 evaluable subjects for stage 1. If ≥33% DLTs are seen during the initial safety lead in, the Safety Committee will convene to consider a dose reduction. If a dose reduction is deemed appropriate, the subjects in the initial safety lead in will need to be replaced and a repeat 6 subject safety lead in will need to be conducted at this lower dose. If 2 or more responses are observed in 12 evaluable subjects, another 14 evaluable subjects will be enrolled for a total of 26 subjects to that cohort. If 6 or more responses are observed, the study has 80% power with alpha of 0.05 to reject the ORR of 10% in favor of the ORR of 30%. Recruitment will stop within a cohort if no more than 1 response is observed after the initial 12 evaluable subjects have been accrued. ORR will be summarized per cohort along with their 95% confidence intervals (CIs). A 2-sided 95% CI will be calculated for the true response rate based on the Clopper-Pearson method.

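### The monotherapy ceiling of 38 cannot be kept together with the per-cohort expansion rule if the optional second monotherapy cohort opens and both cohorts pass Stage 1: the rule then requires 52

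*Combined protocol and SAP*

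**What the plan says.** **Ceilings.** The synopsis (Number of Subjects) gives a part total, "Phase 2a (PLX2853 monotherapy): Up to 38 evaluable subjects", and continues: "There will be up to 2 Simon's 2-stage design cohort of up to 38 evaluable subjects". Section 3.2 has the same sentence with the plural: "There will be up to 2 Simon's 2-stage design cohorts of up to 38 evaluable subjects". The study total is "Total number of subjects: up to 85 evaluable subjects" in the synopsis, and section 3.2 agrees: "Up to 85 evaluable subjects may be enrolled across the study".

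**Other parts.** Phase 1b is planned at about 9 to 15 subjects plus an optional 6, so at most 21. The combination Phase 2a cohort is 12 to 26.

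**Expansion rule.** The synopsis (Statistical Considerations) says: "Each Phase 2a cohort will enroll up to 26 evaluable subjects using a Simon's 2-stage design in which initially 12 evaluable subjects are enrolled". Section 8.6.2.1 applies the same rule. After 2 or more responses in the first 12, "another 14 evaluable subjects will be enrolled for a total of 26 subjects to that cohort". A cohort with 0 or 1 response stops at 12.

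**Second monotherapy cohort.** The synopsis and section 3.1.1 let the Sponsor, at its discretion, add a monotherapy cohort with a Simon two-stage design. It would take subjects with an ARID1A mutation and no known pathogenic PIK3CA, PIK3R1 or PTEN alteration. Neither place makes it depend on the result of the first cohort. Section 7.1.4, on treatment assignment, names a single monotherapy cohort and gives no order for a second.

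**The concern.** The ceiling applies to the monotherapy part as a whole, whereas the expansion rule applies to each cohort and is worded as something that will happen. With one monotherapy cohort the two agree. With two cohorts they agree unless both expand, and then one of them has to give way.

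If the rule gives way, a cohort that met its criterion to continue is cut short, and the stated power does not describe it. If the ceiling gives way, enrolment exceeds the stated maximum. Either choice would be made after Stage 1 responses are known, in an open-label study whose Study Committee may review efficacy about monthly (section 7.1.2).

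**Working it through.** **1. The plan's own figures.** The part ceilings add up: 38 + 21 + 26 = 85. The per-cohort design also reproduces. The probability of success is the sum, over x = 2 to 12, of P(X₁ = x) × P(X₂ ≥ 6 − x), with X₁ binomial on 12 subjects and X₂ binomial on 14. This gives 0.036 at a response rate of 10% and 0.805 at 30%, consistent with the stated alpha of 0.05 and power of 80%.

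**2. Monotherapy totals that the rule can produce.**

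| Cohorts opened | Outcome | Total | Within 38? |
|---|---|---|---|
| One | stops / expands | 12 / 26 | yes |
| Two | both stop | 12 + 12 = 24 | yes |
| Two | one expands | 12 + 26 = 38 | yes |
| Two | both expand | 26 + 26 = 52 | no, 14 over |

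**3. Reading 38 as a per-cohort figure.** This fails. The synopsis gives 38 for the whole part, 85 adds up only with 38 as the part total, and section 8.6.2.1 sets 26 per cohort: "Each Phase 2a cohort will enroll up to 26 evaluable subjects".

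**4. The overall ceiling.** With monotherapy at 52, the other parts may total 85 − 52 = 33 before 85 is passed.
- Phase 1b at its maximum, combination cohort stopped at Stage 1: 52 + 21 + 12 = 85, which is within the ceiling.
- Phase 1b at 9, combination cohort stopped at Stage 1: 52 + 9 + 12 = 73.
- Both other parts at their maxima: 52 + 21 + 26 = 99.

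So 85 is passed only if the combination cohort also goes beyond 12. The figure of 99 is a maximum, not a required enrolment.

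**5. Chance that both monotherapy cohorts pass Stage 1.** A cohort passes with probability 1 − (1 − p)¹² − 12p(1 − p)¹¹. Assume that both cohorts open, with no sequencing condition and independent results.

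| Response rate in both cohorts | One passes | Both pass |
|---|---|---|
| 10% | 0.341 | 0.341² = 0.116 |
| 20% | 0.725 | 0.725² = 0.526 |
| 30% | 0.915 | 0.915² = 0.837 |

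With rates of 10% and 30% the joint chance is 0.341 × 0.915 = 0.312. If the second cohort opened only after the first had stopped, it would be zero. If the first had already expanded, it would be the second cohort's own pass rate. The documents do not give the chance that the second cohort opens. These figures concern the 38 ceiling only.

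**6. Power if the 38 cap is kept.** Two cohorts sharing 38 places leave the smaller with at most 38 ÷ 2 = 19. The calculation is that of step 1 with the second-stage size changed.

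| Final n in the smaller cohort | Responses needed | Type I error at 10% | Power at 30% |
|---|---|---|---|
| 26 (plan) | 6 | 0.036 | 0.805 |
| 19 | 6 | 0.0085 | 0.524 |
| 19 | 5 | 0.034 | 0.708 |
| 12 | 6 | 0.0005 | 0.118 |

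The cut-off of 5 is not in the plan. It is the lowest that holds type I error to 0.05 at n = 19, since a cut-off of 4 gives 0.105. The row for 12 is the case where the first cohort has already reached 26, because 38 − 26 = 12.

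**The case against.** The strongest reply is that 38 was counted on purpose. It is exactly one full cohort plus one stopped at Stage 1 (26 + 12), and 85 follows from it. That points to a plan in which at most one monotherapy cohort expands. The second cohort is a molecularly narrower group, and section 1.4 reports lower sensitivity in ARID1A-mutant cell lines that also carry PIK3CA-pathway mutations, so it could well be a fallback after the broader cohort stops. Opening it is discretionary, so the Sponsor can stay within 38 by not opening it once the first cohort has expanded. Figure 2, which has a monotherapy panel, is not shown in the copy reviewed and may state the condition.

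Much of this stands. It makes an unstated condition more likely than a miscounted sample size, and it limits the confidence that can be placed in the point. It does not reconcile the visible text, because sections 3.1.1, 3.2, 7.1.4 and 8.6.2.1 contain no such condition.

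A second reply is that the text on the optional cohort gives no sizes, and that section 8.6.2.1 later speaks of the monotherapy cohort in the singular. The 12/26 rule is nevertheless stated for each Phase 2a cohort, and no other size is given for the second one.

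A reader might also infer that the same contingency forces enrolment to 99 and so breaks the 85 ceiling. The documents do not support that. Phase 1b and the combination cohort are given as ranges, and with the combination cohort stopped at Stage 1 the total is at most 85.

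**Conclusion.** The conflict is real but confined to one contingency: the optional second monotherapy cohort opens, and both monotherapy cohorts have 2 or more responses in 12. The rule then requires 52 against a ceiling of 38. Once both cohorts are open without a sequencing condition, this is not remote: 12%, 53% or 84% at a common response rate of 10%, 20% or 30%, assuming independence. If the cap is kept, at least one cohort lacks the stated 80% power. At a response rate of 30% its power is at most 52% with the cut-off of 6, and about 12% if it is held at 12.

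A breach of 85 needs a further condition, that the combination cohort also goes beyond Stage 1, and the percentages above do not measure it. Nothing changes for a single-cohort monotherapy part, for the design of the combination cohort, or for the type I error of the full 12/26 design. Confidence is moderate, because Figure 2 is not shown and 38 = 26 + 12 leaves an intended one-expansion rule open. The text should be corrected, since a mandatory rule and a ceiling that cannot both be followed are inconsistent as written.

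**What to change.** Reconcile the synopsis (Number of Subjects and Statistical Considerations), section 3.2 and section 8.6.2.1 in one of two ways, and check that Figure 2 agrees.

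(a) Keep 38 and 85. State that the second monotherapy cohort opens, or expands, only if the other stops at Stage 1. Add that the 80% power does not apply to any cohort that the cap holds below 26. This takes one or two sentences and no extra subjects.

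(b) If both cohorts are meant to be able to expand, restate the maxima as 52 for monotherapy and 99 overall. Each ceiling rises by 14. The extra monotherapy places are used only if both cohorts pass Stage 1, and 99 is reached only if Phase 1b and the combination cohort are also at their maxima.

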3.3 Duration of Study

The study encompasses the following periods:

- Screening Period: Up to 28 days prior to the first dose of study drug
- **Treatment Period:** Daily in 28-day cycles until subject discontinuation or withdrawal or study termination (see Section 7.1.5)
 - Subjects participating in the optional Food Effect sub-study will take a single dose of PLX2853 3 or 4 days prior to C1D1.

- For subjects enrolled in either the monotherapy or combination therapy cohorts, further treatment with either PLX2853 and/or carboplatin will depend on tolerability and clinical benefit as described in Section 7.1.5. In general, for subjects receiving the combination of PLX2853 + carboplatin, it is estimated that subjects will be treated with carboplatin for up to 6 cycles.
- **30-day Follow-up (FU) Visit:** Approximately 30 days after the last dose of study drug or prior to starting any new anti-cancer therapy, whichever occurs first
- Long-term Follow-up Period: Survival follow-up can be via clinic visit, phone call to the subject or referring physician, or other method deemed appropriate by the site and should assess survival, progression, subsequent therapy, and response. Subjects will be followed until death, withdrawal of consent, or loss to follow-up according to the following schedule:
 - First 2 years after the 30-day FU Visit Every 3 months
 - Third year after the 30-day FU Visit and beyond Every 6 months
 - Any subject with a confirmed response who discontinues treatment for reasons other than disease progression will continue to be followed per standard of care and no less than every 3 months until documented disease progression, initiation of a new anti-cancer treatment, or 1 year from discontinuation of study treatment.
 Radiographic scan data will be collected and if scan data are not available, a scan will be obtained every 3 months until 6 months of radiographic follow-up after confirmed response has been obtained.

3.4 Study Endpoints

3.4.1 Primary Endpoints

The primary endpoints are as follows:

- Phase 2a (PLX2853 monotherapy): overall response rate (ORR) as measured by Response Evaluation Criteria in Solid Tumors Version 1.1 (RECIST v1.1)
- Phase 1b (PLX2853 + carboplatin combination): establish the MTD/RP2D for the combination of PLX2853 + carboplatin
- Phase 2a (PLX2853 + carboplatin combination): ORR as measured by RECIST v1.1

3.4.2 Secondary Endpoints

The secondary endpoints are as follows:

• Incidence of treatment-emergent adverse events (TEAEs), changes in safety parameters, and unacceptable toxicities

- DOR
- Disease control rate (DCR)
- Progression-free survival (PFS)
- Overall survival (OS)
- PLX2853 PK parameters following single and repeated dosing

3.4.3 Exploratory Endpoints

The exploratory endpoint is as follows:

• Analysis of peripheral blood and tumors for dose- and exposure-dependent changes in the expression of BET target genes

3.5 Randomization

None of the subjects in this study will be randomized.

4.0 STUDY POPULATION

Subjects must meet the following inclusion and exclusion criteria to be enrolled in the study.

4.1 Inclusion Criteria

- 1. Age \geq 18 years at the time of signing informed consent
- 2. Histologically or cytologically confirmed diagnosis of 1 of the following and must have measurable disease per RECIST v1.1:
 - Phase 2a (PLX2853 monotherapy): Any advanced gynecological malignancy (cervical, vaginal, vulvar, uterine, ovarian, fallopian tube, or primary peritoneal) with a known ARID1A mutation, that is intolerant to or refractory to all standard therapy known to confer clinical benefit.
 - Subjects must have tumor accessible for sequential biopsy and be willing to provide on-study tumor tissue biopsy (core needle biopsy or excision required). Tissue collection must not constitute a significant risk procedure. A significant risk procedure is generally considered to be one for which the procedure associated absolute risk of mortality or major morbidity in the patient's clinical setting and at the institution completing the procedure is 2% or higher. When possible, newly obtained tissue should be collected from a non-target lesion.

• Phase 1b and Phase 2a (PLX2853 + carboplatin combination):

Platinum-resistant EOC (including fallopian tube or primary peritoneal cancer). Platinum-resistant is defined as disease that may have responded to a platinum-containing chemotherapy regimen, but there is documentation of demonstrated recurrence within 6 months following the completion of that platinum-containing regimen.

OR

Subjects with platinum-refractory EOC are eligible, provided refractory outcome was to second line or later repeated platinum regimen (not first line). Refractory is defined as disease that failed to achieve at least a PR to a platinum-containing regimen (i.e., SD or actual disease progression).

Progressive disease of EOC following platinum-based therapy can be documented by physical examination, computed tomography (CT) scans, or a doubling of cancer antigen 125 (CA-125) levels from either 1) upper limit of normal (ULN) or 2) most recent nadir value (per the Rustin criteria [Rustin 2011] [Appendix 6]). For CA-125 to be used as a criterion for progressive disease, the CA-125 level nadir must have been above the ULN. In addition, the CA-125 nadir level must have been confirmed by a second measurement at least 1 week after the initial measurement.

- Subjects in Phase 2a must have tumor accessible for sequential biopsy and be willing to provide on-study tumor tissue biopsy (core needle biopsy or excision required). Tissue collection must not constitute a significant risk procedure. A significant risk procedure is generally considered to be one for which the procedure associated absolute risk of mortality or major morbidity in the patient's clinical setting and at the institution completing the procedure is 2% or higher. When possible, newly obtained tissue should be collected from a non-target lesion.
- 3. Eastern Cooperative Oncology Group (ECOG) Performance Status 0 to 1
- 4. Adequate organ function as demonstrated by the following laboratory values. All Screening laboratory tests should be performed within 10 days of the first PLX2853 dose. Subjects must meet the following eligibility criteria prior to dosing:
 - Hematological:
 - Neutrophils ≥1500/μL
 - Platelets \geq 100,000/µL
 - Hemoglobin ≥9 g/dL (transfusion and erythropoietin not permitted within 14 days prior to blood draw)

• Renal:

- Estimated glomerular filtration rate (GFR) (Chronic Kidney Disease Epidemiology Collaboration [CKD-EPI] creatinine calculation [Appendix 1]) ≥60 mL/min/1.73 m²
- Hepatic:
 - Serum total bilirubin ≤1.5 × ULN OR
 - Direct bilirubin ≤ULN for subjects with total bilirubin >1.5 × ULN

Exception for elevated bilirubin secondary to Gilbert's disease, in which case it must be ≤2.5 mg/dL. Confirmation of Gilbert's diagnosis requires: elevated unconjugated (indirect) bilirubin values; normal complete blood count in previous 12 months, blood smear, and reticulocyte count; normal aminotransferases and alkaline phosphatase in previous 12 months

- Aspartate aminotransferase (AST) and alanine aminotransferase (ALT) $\leq 2.5 \times \text{ULN}$
- Gamma-glutamyl transferase ≤3 × ULN
- Coagulation:
 - International normalized ratio $\leq 1.5 \times ULN$
 - aPTT ≤1.5 × ULN

- Chemistry:
 - Albumin ≥3.0 g/dL
- 5. Women of child bearing potential (defined as any female who has experienced menarche and who has not undergone successful surgical sterilization [hysterectomy, bilateral tubal ligation, or bilateral oophorectomy] or is not postmenopausal) must have a negative serum pregnancy test within 7 days prior to taking the first dose of study drug and, if sexually active, must agree to use a highly effective method of contraception (a contraception method with a failure rate <1% per year) and 1 additional barrier method from the time of the negative pregnancy test to 90 days (for subjects in the United States (US)) or 6 months (for subjects in Canada) after the last dose of study drug. Women of non-child bearing potential may be included if they are either surgically sterile or have been postmenopausal for ≥1 year.
- 6. Except as specified above for organ function, all drug-related toxicity from previous cancer therapy must be resolved (to Grade ≤1 or baseline per NCI CTCAE v5.0) prior to study treatment administration (Grade 2: alopecia, hot flashes, decreased libido, immuno-oncology drug induced hypothyroidism controlled with medication, or neuropathy is allowed).
- 7. Willingness and ability to provide written informed consent prior to any study-related procedures and to comply with all study requirements

